1. SYNOPSIS

Study title	Verona coronary physiology interventional registry (VR-CP)
Protocol version	V1
Date	March, 1 st 2025
Study sponsor	Azienda Ospedaliera Universitaria Integrata di Verona
Study principal investigator	[name] MD PhD
Patient population	The observational Verona Coronary Physiology Interventional Registry (VR-CP) study enrolls patients with suspected coronary artery disease who underwent coronary angiography with functional assessment (coronary physiology).
Primary objective	The primary objective is to assess the functional characteristics of coronary lesions documented during coronary angiography and correlate them with the risk of cardiovascular events during follow-up.
Secondary objective	
- To examine the prognostic value of physiological parameters (FFR and angiography-derived FFR).- To analyze the clinical, demographic, and angiographic characteristics of patients with coronary lesions assessed by coronary physiology parameters, in order to identify high-risk subgroups.- To correlate coronary physiology values with angina symptoms.- To compare invasive FFR with angiography-derived FFR.- To compare clinical outcomes between patients managed conservatively and those undergoing invasive interventions.
Study design	The VR-CP study is a single-center observational study enrolling consecutive patients with coronary stenoses documented during coronary angiography and functionally assessed with coronary physiology (fractional flow reserve [FFR] or angiography-derived FFR) performed for suspected ischemic heart disease. Follow-up is conducted, after obtaining informed consent, through telephone contact and/or outpatient visits. Adverse events are adjudicated by an independent clinical events committee, blinded to clinical data.
Data source	The selection of eligible patients is extracted from registries and the analysis of coronary angiographic studies performed from January 2010 to December 2024.
Sample size	Enrollment will include approximately 1,000 patients evaluated with FFR or angiography-derived FFR. This sample size will allow for subgroup analyses stratifying lesions by functional severity based on FFR values.
Inclusion criteria	
- Coronary angiography with functional assessment by FFR or angiography-derived FFR (index procedure)- Provision of written informed consent- Age \geq18 years old at the time of the index procedure

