Consequently, invasive wire-based solutions for physiological assessment were developed to identify ischemia-producing epicardial coronary stenoses [3, 8]. Current European guidelines emphasize the importance of performing physiological assessment for all intermediate coronary artery stenoses, including left main stenosis, side branch stenosis and serial stenoses, when functional information from non-invasive tests is lacking [9]. Moreover, in patients with multivessel CAD, PCI guided by fractional flow reserve (FFR) results in an improved outcome irrespective of available non-invasive functional test results [9]. The development of FFR and its use in guiding percutaneous intervention, has led to improved patient outcomes compared with angiography guidance alone [10]. New developments in wire-free functional coronary assessment derived from the angiogram, globally termed as functional coronary angiography (FCA), may contribute to a more widespread use of physiology to diagnose the cause of ischemia and to plan and guide coronary revascularization [11–16]. These systems are based on vessel lumen reconstructions from coronary angiography, with the aim of providing FFR-like estimates of stenosis severity, whilst not requiring pharmacological agents or intracoronary instrumentation. Different software approaches to FFR estimation derived from coronary angiography have been developed. Several studies demonstrated the good correlation between wire-based and Angiography-derived FFR with a cut-off of 0.80. In a recent meta-analysis of 16 studies, 819 patients and 969 vessels with paired FFR and Angiography-derived FFR were included. Authors found an overall satisfactory agreement (mean difference 0.009 ± 0.068 , $I^2 = 39.6$) of angiography- and wire- derived FFR. The diagnostic performance was sensitivity 84% (95%CI: 77-90, $I^2 = 70.1$), specificity 88% (95%CI: 84-91, $I^2 = 60.1$); positive predictive value 80% (95%CI: 76-85, $I^2 = 33.4$), and negative predictive value 95% (95%CI: 93-96, $I^2 = 75.9$) [15]. Several non-inferiority trials are ongoing to provide the data answer regarding Angiography-derived FFR clinical equivalence in comparison with wire-based FFR

(Tab.I). Angiography-derived FFR analyzability depends on quality of angiography, and it is feasible in around 80% of the cases.

The Vulnerable Plaque: Pathophysiology of Coronary Artery Disease Progression

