5. POPULATION

Inclusion Criteria

- Previous coronary angiography with assessment of FFR and/or angiography-derived FFR.
- Age \geq 18 years old*
- Provision of written informed consent.

* At the time of the index coronary angiography.

Exclusion Criteria

- Inability to provide informed consent to participate in the study.
- Age $<$ 18 years old*

* At the time of the index coronary angiography.

Vulnerable Populations

The following subjects will not be eligible for inclusion:

- Pregnant women
- Women who are breastfeeding

Criteria for Early Withdrawal from the Study

Subject's request to withdraw participation

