11. SAMPLE SIZE CALCULATION

In contemporary clinical trials on coronary physiology indices, the composite adverse event rate at 12 months follow-up is relatively low, ranging from 6.1% in the SWEDEHEART-IFR study to 6.7% in the DEFINE-FLAIR study. Therefore, assuming a type I error of 0.05 and a statistical power of 80%, the study should include 1000–1200 patients to generate a sufficient number of evaluable events. This sample size will also allow for subgroup analyses stratifying lesions by functional severity based on FFR values.

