15. DEFINITIONS

Ischemia-driven target vessel revascularization (TVR)

All ischemia-driven revascularizations refer to the target lesion that led to enrollment into the study.

Requires the following criteria:

- Ischemic symptoms consistent with CCS class ≥ 3 angina despite optimal medical therapy

AND

- PCI or CABG of either the target that led to enrollment into the study PLUS at least ONE of the following:
 - Positive functional study (Exercise or myocardial perfusion imaging or stress or dobutamine echo) demonstrating clear evidence of reversible ischemia corresponding to a stenosis in the target vessel;
 - New ischemic ECG changes (ST-segment depression ≥ 1 mm, ST-segment elevation ≥ 1 mm or T wave inversion ≥ 2 mm) at rest or with exertion in a distribution consistent with a stenosis in the target vessel;
 - FFR ≤ 0.80 , iFR ≤ 0.89 , cFFR ≤ 0.85 , Angiography-derived FFR ≤ 0.80 in the target vessel.

Vessel-related myocardial infarction (MI)

MI is defined according to the 4th universal definition of myocardial infarction. The leading symptom that initiates the diagnostic and therapeutic cascade in patients with suspected MI is chest pain. Based on the electrocardiogram (ECG), two groups of patients should be differentiated: Patients with acute chest pain and persistent (>20 min) ST-segment elevation. This condition is termed ST-elevation ACS and generally reflects an acute total coronary occlusion. Most patients will ultimately develop an ST-elevation myocardial infarction (STEMI). The mainstay of treatment in these patients is immediate reperfusion by primary angioplasty or fibrinolytic therapy.

Patients with acute chest pain but no persistent ST-segment elevation. ECG changes may include transient ST-segment elevation, persistent or transient ST-segment depression, T-wave inversion, flat T waves or pseudo-normalization of T waves or the ECG may be normal. The clinical spectrum of NSTEMI may range from patients free of symptoms at presentation to individuals with ongoing ischemia, electrical or hemodynamic instability or cardiac arrest.

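### Severity strata are set on FFR values in a sample that may enter by wire or angiography-derived FFR, with no rule for which value counts and no mandatory adjustment for test type

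*Protocol*

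**What the plan says.** Under the inclusion criteria in Section 5, either measurement qualifies a patient: "Previous coronary angiography with assessment of FFR and/or angiography-derived FFR". The Synopsis counts the sample in the same way: "Enrollment will include approximately 1,000 patients evaluated with FFR or angiography-derived FFR". Its next sentence, repeated in Section 11, says that this sample size permits "subgroup analyses stratifying lesions by functional severity based on FFR values". Neither place names the index, a stratum cut-off, or a rule for patients who have both values.

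Elsewhere the two indices are sometimes joined and sometimes kept apart. Section 7 writes them with a slash, as one parameter to be correlated with angina scores. The TVR definition in Section 15 uses the wire FFR threshold of 0.80 again for the second index ("Angiography-derived FFR ≤ 0.80 in the target vessel"), while iFR and cFFR have thresholds of their own. Section 4, by contrast, lists the two indices separately and makes their comparison a secondary objective.

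Section 12 does not mention test type. Covariates enter the multivariable Cox model only if their univariate p-value is below 0.1.

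**The concern.** If the strata cover the whole sample, a lesion's stratum depends partly on which test was done. Patients with both tests could be placed in either of two strata, and the planned comparison of the indices requires that such patients exist. If FFR values means wire FFR only, patients with angiography-derived FFR alone have no stratum, and the full sample does not support the strata as claimed. Both readings leave the exposure unsettled.

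Two things are at stake. One is scatter: per-vessel disagreement between the tests moves lesions across the cut-off and tends to flatten the gradient between FFR and VOCE, if risk follows wire FFR. The other is confounding: test type is unlikely to be random. The Introduction says that angiography-derived FFR depends on image quality and calls wire-free assessment a new development, while index procedures run from 2010 to 2024. Test type may therefore track calendar period, follow-up length and standard of care. A univariate significance screen is a weak safeguard, because a confounder can fail it.

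**Working it through.** **Inputs.** The Introduction supports "good correlation between wire-based and Angiography-derived FFR with a cut-off of 0.80" with a meta-analysis in which "819 patients and 969 vessels with paired FFR and Angiography-derived FFR were included". It gives "sensitivity 84% (95%CI: 77-90"), specificity 88% (84-91), PPV 80%, NPV 95%, and a mean difference of 0.009 ± 0.068, where I read the ± as a standard deviation. Analysability of angiography-derived FFR is about 80%. Section 11 gives 12-month event rates of 6.1% and 6.7%, and 1,000-1,200 patients. The plan has no figure of its own for disagreement between the tests, so there is none to reproduce. It states no stratum cut-off either; 0.80 is assumed below.

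**1. Limits of agreement.** 0.009 ± 1.96 × 0.068 = -0.124 to +0.142.

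**2. Discordance at 0.80.** With p the share of vessels at or below 0.80 by wire, discordance = p × (1 - 0.84) + (1 - p) × (1 - 0.88).
- The stated PPV implies p = 0.364, giving 0.364 × 0.16 + 0.636 × 0.12 = 13.5%.
- The stated NPV implies p = 0.224, giving 0.224 × 0.16 + 0.776 × 0.12 = 12.9%.
- For p from 0.20 to 0.50 the range is 12.8% to 14.0%. At the joint confidence limits of sensitivity and specificity it is about 9% to 19%.

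The four accuracy figures do not fit a single 2×2 table (implied p of 36% against 22%), but discordance is about 13% under either value.

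**3. Effect on a pooled dichotomy.** With wire FFR as reference and non-differential error, the share of the true risk difference that survives is PPV + NPV - 1. PPV and NPV are computed here from sensitivity, specificity and p.

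Assume that half the lesions have only angiography-derived FFR, independently of severity, and that the rest are classed by wire without error. Effective sensitivity is (1 + 0.84)/2 = 0.92 and effective specificity (1 + 0.88)/2 = 0.94.

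| p | Misclassified, 50% angiography only | Kept, 50% angiography only | Misclassified, all angiography | Kept, all angiography |
|---|---|---|---|---|
| 0.30 | 6.6% | 0.868 + 0.965 - 1 = 83% | 13.2% | 0.750 + 0.928 - 1 = 68% |
| 0.40 | 6.8% | 0.911 + 0.946 - 1 = 86% | 13.6% | 0.824 + 0.892 - 1 = 72% |
| 0.50 | 7.0% | 0.939 + 0.922 - 1 = 86% | 14.0% | 0.875 + 0.846 - 1 = 72% |

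In counts at p = 0.30, if 25%, 50% or 75% of 1,000 lesions had angiography-derived FFR only, about 33, 66 or 99 of them would sit in a different stratum from the one wire FFR would give (250, 500 or 750 × 0.132).

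**4. Precision if analysed by test.** Expected 12-month events run from 1,000 × 0.061 = 61 to 1,200 × 0.067 = 80. The smallest hazard ratio detectable with 80% power at two-sided 0.05 (Schoenfeld) is exp[(1.960 + 0.842)/√(d × a(1 - a))], where d is the number of events and a the share of lesions in one stratum, taken as 0.36 to 0.50.
- Pooled, d = 61 to 80: hazard ratio 1.9 to 2.1.
- Per test with a 50:50 split, d = 30.5 to 40: from exp(2.802/√(40 × 0.25)) = 2.4 to exp(2.802/√(30.5 × 0.2304)) = 2.9.

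Section 12 counts events over the whole follow-up, so actual event numbers should be higher and these hazard ratios smaller.

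**The case against.** The strongest reply is that pooling is inferred. The Section 11 clause is a closing remark about sample size, not a definition of the primary exposure. The primary objective in Section 4 speaks only of functional characteristics, and a protocol that sets out to compare two indices hardly assumes that they are interchangeable. This stands as a limit on the claim: the protocol never says that it pools. It does not remove the ambiguity, because the objective that separates the indices is secondary, and the strata and the primary objective name neither.

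A second reply is that precedence rules and model terms belong in a SAP. For the precedence rule alone I would agree. But Section 12 already fixes how covariates are chosen, and under that rule test type can drop out.

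A third concerns size. A reader might infer that a quarter to a third of the effect is lost. The 68-72% figures hold only if every lesion is classed by angiography-derived FFR, which the protocol does not plan. Adding the quoted PPV and NPV directly would give 75%, but those two figures imply different prevalences. A reader might also note that a vessel with wire FFR of 0.82 has a 33-44% chance of reading at or below 0.80 by angiography. That is true only so close to the cut-off: at 0.85 the chance is 19-27%, and overall discordance is about 13%. The mean bias of 0.009 is small, so this is scatter rather than a shift.

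Finally, wire FFR as truth is a convention. Discordance does not show which index predicts VOCE better, and the protocol makes the prognostic value of both an objective. Section 13 concedes that techniques changed over time, but does not name test type as a source of bias.

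**Conclusion.** The point holds in limited form. The severity strata rest on an exposure that the protocol leaves ambiguous, and Section 12 does not guarantee that test type is accounted for. By the protocol's own figures the two measurements disagree at 0.80 in about 13% of vessels (plausibly 9-19%).

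The consequence for a pooled result cannot be fixed from the document, because the share with angiography-derived FFR alone is not given. At a 50% share, about 7% of lesions would be misclassified and about 83-86% of the risk difference kept. That rests on four assumptions: the share, its independence from severity, wire FFR as an error-free reference, and a split at 0.80. The 68-72% is a limit, not an expectation.

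The documents do not support saying that the plan declares the indices interchangeable, or that the primary result is shown to be biased. Confounding by test type is a reasonable risk over a 15-year enrolment window, not a demonstrated fact.

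**What to change.** In Sections 11 and 12:

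- State which index value defines the severity stratum and which takes precedence when both exist, and replace the bare reference to FFR values accordingly.
- Stratify the primary Cox model by test type, whatever the univariate p < 0.1 screen shows.
- Report the test-type by FFR interaction as exploratory.
- Show the severity strata by test type beside the pooled result.
- Consider a sensitivity analysis on one common angiography-derived scale. Section 6 keeps the initial angiograms for functional analysis, and at the protocol's figure of about 80% analysable this would cover roughly 800 of 1,000 patients.

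Stratifying the model removes differences in baseline risk between the tests; it does not correct the scatter. The test-specific displays and the sensitivity analysis show how much the scatter matters.

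The cost is mostly wording, since Section 6 already has the FFR and angiography-derived FFR data recorded; the sensitivity analysis adds reading time. Test-specific estimates will be clearly less precise: the smallest detectable hazard ratio is about 2.4-2.9 per test against 1.9-2.1 pooled, assuming a 50:50 split and 12-month events only. The pooled, test-stratified model should therefore remain primary.

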12. STATISTICAL ANALYSIS

Continuous variables will be tested for normal distribution using the Kolmogorov-Smirnov test.

Variables with a normal distribution will be presented as mean \pm standard deviation and compared using t-tests and one-way ANOVA. Otherwise, median [interquartile range] will be used, and comparisons will be performed using the Mann-Whitney U and Kruskal-Wallis tests. Categorical variables will be summarized as absolute and relative frequencies (percentages) and compared using the χ^2 test. Correlations between variables will be evaluated using linear and logistic regression analyses. The level of statistical significance will be set at $\alpha = 0.05$. Kaplan-Meier curves will be plotted to describe event-free survival, and differences between groups will be tested using the log-rank test. The primary analysis will be based on events occurring during the entire follow-up period for each patient at database lock. Any confounding factors will be tested using Cox regression models. Variables with a p-value < 0.1 in univariate analysis will be included in a multivariate analysis to identify independent predictors. When appropriate, 95% confidence intervals will be calculated.

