Exclusion Criteria	
- Inability to provide informed consent to participate in the study
Informed Consent	Patients identified as eligible for the protocol will be invited to provide informed consent for participation in the retrospective study through contact by telephone, e-mail, mail, or during an outpatient visit.
Study Procedures	Once eligibility for the protocol is confirmed, informed consent is requested and obtained. After enrolment, the angiographic images from the index coronary angiography are analysed by the investigators. Long-term follow-up is performed by monitoring the clinical status and recording major adverse cardiac events through review of medical records, outpatient visits, or telephone contacts.
Primary Endpoint	Composite of vessel-oriented composite endpoint (VOCE), including target vessel revascularization (TVR), target vessel-related myocardial infarction (MI), and cardiovascular death.
Secondary Endpoints	
- Individual components of the primary endpoint- Hospitalization for unstable angina- Angina status (Seattle Angina Questionnaire)- Number of prescribed antianginal medications
Study Duration	Patients are retrospectively enrolled from January 2010 to December 2024. Clinical contact (medical records, outpatient visits, telephone communication) is periodically collected recording longitudinal data at 12-month intervals.
Clinical Event Adjudication Committee	The following events are adjudicated by an independent committee blinded to clinical data: TVR, target vessel-related MI, cardiovascular death, and hospitalization for unstable angina.

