3. STUDY DESIGN

The Verona Coronary Physiology Interventional Registry (VR-CP) study is a single-center, single-arm, observational study with blinded event adjudication. VR-CP enrolls patients who underwent coronary angiography for suspected ischemic heart disease, in whom at least one coronary lesion was identified and functionally assessed by coronary physiology testing (fractional flow reserve [FFR] or angiography-derived FFR).

Eligible patients are identified through registry data and review of coronary angiographic studies performed from January 2010 to December 2024. Patients meeting inclusion criteria are invited to provide written informed consent to participate in the observational study. Recruitment may occur through telephone, mail, email, or during outpatient visits. All study data are recorded in an anonymized electronic case report form (eCRF).

The follow-up involves periodic recording of the clinical status and reporting of any adverse events through review of medical records, outpatient visits, or telephone communications, in order to ensure longitudinal data collection at 12-month intervals.

Adverse events are adjudicated by an independent Clinical Event Committee (CEC) blinded to all patient clinical data. Investigators will provide the CEC with anonymized clinical documentation relating to the reported adverse event. The CEC will adjudicate events that are part of the study's primary and secondary endpoints. Event definitions and adjudication rules are established by the

Principal Investigators and recorded in the Adjudication Committee Charter. The adjudication outcomes determined by the CEC will be used for the final statistical analysis.

CEC members will be appointed by the Principal Investigator at the time of study activation. They will be selected among experienced cardiologists with no access to the clinical documentation of enrolled patients.

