7. ENDPOINTS

Primary Endpoint

The primary endpoint is the composite risk of vessel-oriented composite endpoint (VOCE), including target vessel revascularization (TVR), vessel-related myocardial infarction (MI), and cardiovascular death.

Secondary Endpoint

- Individual components of the primary endpoint.
- Hospitalization for unstable angina.
- Angina status assessed using the Seattle Angina Questionnaire (SAQ). The SAQ will be used to evaluate patients' quality of life and the impact of angina symptoms over time. Scores from the main subscales (physical limitation, angina stability, angina frequency, treatment perception, and overall quality of life) will be analysed to correlate symptom severity with coronary physiology parameters (e.g., FFR/angiography-derived FFR).
- Number of prescribed antianginal drugs. The number of prescribed antianginal medications will be monitored to assess the intensity of pharmacological treatment required during follow-up. This parameter will serve as a proxy for residual disease severity and will allow comparison between patients managed conservatively and those treated with invasive interventions.

[figure not shown]

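### SAQ scores and antianginal drug number are followed over time, but Section 12 names only independent-observation methods for them and fixes no analysis time point or per-patient summary

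*Protocol*

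**What the plan says.** **Endpoints.** Protocol Section 7 lists both outcomes as secondary endpoints and describes each as something followed over time.

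- SAQ: "The SAQ will be used to evaluate patients' quality of life and the impact of angina symptoms over time". The subscale scores "will be analysed to correlate symptom severity with coronary physiology parameters".
- Antianginal drugs: "The number of prescribed antianginal medications will be monitored to assess the intensity of pharmacological treatment required during follow-up". The same item says the count will be used to compare conservatively and invasively managed patients.

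**Follow-up.** Section 3 states: "The follow-up involves periodic recording of the clinical status and reporting of any adverse events". The sentence ends "in order to ensure longitudinal data collection at 12-month intervals". The synopsis says that clinical contact is "periodically collected recording longitudinal data at 12-month intervals". Section 10 continues follow-up to a 10-year evaluation. None of these places gives time points for the SAQ or the drug count.

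**Methods.** For outcomes that are not time-to-event, Section 12 names t-tests, one-way ANOVA, Mann-Whitney, Kruskal-Wallis and chi-square tests. For association it says: "Correlations between variables will be evaluated using linear and logistic regression analyses". Kaplan-Meier, log-rank and Cox methods are also named, but they serve events. An analysis window (all follow-up to database lock) is given only for the event-based primary analysis.

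**The concern.** Read together, Sections 7 and 12 send the SAQ–physiology association to ordinary regression and the drug-count comparison to two-group tests. As named, these methods take each row as an independent observation. Scores from one patient in successive years are not independent, and the number of records is likely to differ between patients.

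Section 12 does not say how several records per patient become an analysis. The analyst could stack all records, choose one visit, or average, and could choose after seeing the data. These routes differ in error rate and in what they can show. Two secondary objectives depend on the choice: the relation of physiology to angina, and the outcomes of conservative versus invasive management.

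**Working it through.** **The plan's own figure.** There is none for these endpoints. The 1000–1200 patients in Section 11 are justified by event rates and do not bear on this point.

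**Inputs**
- Significance level 0.05, from Section 12; two-sided testing is assumed because sidedness is not stated.
- Records per patient, k = 2, 5 or 10: assumed. Ten corresponds to annual records over the 10 years of Section 10.
- Within-patient correlation, ρ = 0.3 to 0.7: assumed; the protocol gives none.
- Equal k for all patients, equal correlation between any two visits, and an exposure fixed per patient (index physiology or index management).

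**Route 1: all records entered as independent rows**

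Design effect D = 1 + (k − 1)ρ. The naive standard error is 1/√D of the true one. Actual type I error = 2[1 − Φ(1.96/√D)].

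Worked case, k = 5 and ρ = 0.5: D = 1 + 4 × 0.5 = 3.0; 1/√3.0 = 0.58; 1.96/√3.0 = 1.13; type I error = 0.258.

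| k | ρ | D | naive SE / true SE | type I error | k/D |
|---|---|---|---|---|---|
| 2 | 0.3 | 1.3 | 0.88 | 0.086 | 1.54 |
| 2 | 0.5 | 1.5 | 0.82 | 0.110 | 1.33 |
| 2 | 0.7 | 1.7 | 0.77 | 0.133 | 1.18 |
| 5 | 0.3 | 2.2 | 0.67 | 0.186 | 2.27 |
| 5 | 0.5 | 3.0 | 0.58 | 0.258 | 1.67 |
| 5 | 0.7 | 3.8 | 0.51 | 0.315 | 1.32 |
| 10 | 0.3 | 3.7 | 0.52 | 0.308 | 2.70 |
| 10 | 0.5 | 5.5 | 0.43 | 0.403 | 1.82 |
| 10 | 0.7 | 7.3 | 0.37 | 0.468 | 1.37 |

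Coverage of a nominal 95% interval is one minus the type I error: 0.742 in the worked case and 0.532 in the worst row.

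A simulation (1000 patients, two equal groups, 2000 runs per setting) agrees. For k = 5 and ρ = 0.5, stacked rows gave 0.245 against 0.258 by formula.

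**Route 2: one visit per patient**

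The independence assumption holds; simulated type I error was 0.049–0.058. The information forgone on a constant effect, relative to using all k visits, is k/D (last column). At ρ = 0.5–0.7 with 5 or 10 visits this is 1.32–1.82. One visit cannot describe change over time.

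**Route 3: one mean per patient**

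Simulated type I error was 0.045–0.058 with the same t-test, and every visit contributes. A mean does not describe change over time either.

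**The case against.** The strongest reply is that this belongs to the statistical analysis plan, which is not at hand. The handling of repeated records for secondary endpoints is often settled there, and a protocol that names no mixed model is not wrong for that reason alone. That stands as far as it goes. But Section 12 is not silent: it assigns correlations to ordinary regression and goes into detail such as the normality test and the p < 0.1 selection rule. The point is that the stated methods, as named, do not fit outcomes that Section 7 follows over time.

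Three stronger readings are tempting, and the protocol does not support them.

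- **That SAQ and drug count are recorded every 12 months.** Section 3 attaches that interval to clinical status and adverse events, and the synopsis to clinical contact. Section 7 says only that the two outcomes are followed over time and during follow-up. Repetition is stated; frequency is not. Index procedures run from 2010 to 2024 and the protocol is dated March 2025. If SAQ collection starts at consent, patients indexed in 2010–2014 are at or near year 10 already and could contribute few scores. Drug counts may be recoverable from records. The 2-visit rows may therefore be nearer the truth for many patients' SAQ scores than the 10-visit rows.
- **That the protocol will pool records as independent rows.** It does not say so, and linear or logistic regression can carry cluster-robust standard errors. The inflated error rates are conditional on pooling.
- **That the only outcomes are wrong standard errors or most of the data unused.** Route 3 is valid and uses every visit. Even one visit keeps about 55–76% of the information on a constant effect (1/1.82 to 1/1.32) in the 5- to 10-visit cases at correlation 0.5–0.7.

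**Conclusion.** The point holds as a gap between Section 7 and Section 12: outcomes followed over time, methods for independent observations, and no rule linking the two.

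Its size depends on what is done with the records. Entered as independent rows, they give a false-positive rate of about 9–13% (2 visits), 19–31% (5) or 31–47% (10) instead of 5%, for assumed correlation 0.3–0.7 and equal visits. Reduced to one visit, they give valid tests, but change cannot be described, and 1.3–1.8 times the information on a constant effect is forgone at correlation 0.5–0.7 with 5–10 visits. The visit counts, the correlation and the pooling are assumptions.

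Only secondary endpoints are affected; the primary VOCE analysis is not. The change is worth making because it is cheap and removes a choice that could otherwise be made after seeing the data.

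**What to change.** In Section 12:

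- Analyse each SAQ scale with a linear mixed model: a random intercept for patient, and fixed effects for time since index and index physiology.
- Put index management in a separate, labelled model, or use it as the exposure for the conservative-versus-invasive comparison. Sections 6 and 8 say that physiology guided management, so adjusting for management changes the question to an association conditional on treatment.
- Analyse antianginal drug number with a patient-clustered count or ordinal model (GEE).
- Report estimates with 95% confidence intervals.
- Keep t-tests, ANOVA and rank tests for analyses with one value per patient: baseline, one pre-specified time point, or a pre-specified per-patient summary. They need not be confined to baseline.

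Stating when the SAQ and the drug count are recorded would make these rules concrete. The cost is a few sentences in the protocol or analysis plan and slightly more analysis work; no new data are needed.
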